★ Patients will be stratified at baseline based on whether they are naïve to TNF α inhibitors or had an inadequate response (including intolerance) to TNF α inhibitors.

R+ = responder, i.e. patient with spinal pain NRS score < 4

R- = non-responder, i.e. patient with spinal pain NRS score \geq 4

axSpA=axial spondyloarthritis, BSL=baseline, PE=primary endpoint, SE=secondary endpoint, TNF α =tumor necrosis factor alpha, TNF α -IR=tumor necrosis factor α inadequate responder, W=week

Primary analysis time point

The primary analysis will be performed based on Week 8 assessment data. Average spinal pain NRS score will be considered as primary endpoint and will be analyzed for all applicable variables.

Interim analyses

No interim analysis is planned for this study.

The statistical analysis will be performed after all the patients have completed the study. Once all the data are complete and clean, the database will be locked and analyzed.

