2.5.4 Sensitivity analyses

The average spinal pain and raw (total and nocturnal spinal pain separately) NRS scores will be analyzed using a repeated measures analysis of variance (ANOVA) model. The model will include the same factors as the logistic model of primary analysis plus the respective baseline score as a covariate. Analysis visit will be used as repeat factor.

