2.13 Other Exploratory analyses

All the exploratory efficacy evaluation will be performed on FAS-TP1 and FAS-TP2 population based on the corresponding treatment periods. Refer to [Table 1.2-1](#) of Section 1 for the list of exploratory endpoints.

The following exploratory efficacy variables will be analyzed on the FAS-TP1 and FAS-TP2 population at (Baseline to Week 8) and (Week 8 to Week 24) respectively for all applicable analysis visits unless otherwise specified.

- Spinal pain score: Average NRS spinal pain score will be calculated only if total and nocturnal pain score are non-missing.
- BASDAI score: It will be calculated based on the average of the non-missing answers available.
- ASDAS CRP
- Patient reported outcomes: FACIT-Fatigue[©], PASS, ASAS health index

- The average and raw (total and nocturnal) spinal pain NRS scores will be analyzed using a repeated measures analysis of variance (ANOVA) model with treatment, country and the stratification factor of prior exposure to TNF inhibitors (naïve/ inadequate responders to TNF α inhibitors) as factors and respective baseline NRS score as covariate. The least squares means of the two treatment groups, least squares mean difference and 95% confidence interval for the difference in the two treatment groups will be presented along with the p-value based on the fitted linear model.
- Formula for ASDAS-CRP calculation: ASDAS (CRP) = 0.121 x total back pain + 0,110 x patient global + 0.073 x peripheral pain/swelling + 0.058 x duration of morning stiffness + 0.579 x LN (CRP+1)
The parameters, which are taken from patient reported outcomes, are expected to have values 0-10. CRP needs to be in the unit mg/L.

All endpoints relating to exploratory objectives will be summarized descriptively. Summary statistics will include relative and absolute frequencies for the categorical variables and the number of patients (n), minimum, mean, median and maximum for continuous variables will be separately provided for both period I and period II. Time courses of response rates and mean NRS-scores will be displayed graphically.

The following categorical exploratory endpoints will also be summarized categorically as absolute and relative frequencies (proportions, %). Any improvement or reduction is referred to as 'response' for all the below mentioned endpoints.

- Proportion of patients in each treatment group with response in spinal pain score < 4 at Week 1, 2, 3 and 4.

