5.4 Statistical models

5.4.1 Primary analysis

The null hypothesis to be rejected is that the odds of response at Week 8 are equal in both treatment groups. The corresponding alternative hypothesis is that the odds of response at Week 8 are higher under secukinumab compared to placebo.

The primary analyses will be conducted via logistic regression model with treatment, country and the stratification factor of prior exposure to TNF inhibitors (naïve/ inadequate responders to TNF α inhibitors) as factors. The Odds ratio, 95% confidence interval (CI) and p-value will be presented comparing secukinumab 150 mg treatment group to placebo group at Week 8.

SAS Code for logistic model

```
Proc logistic data=aaa;
Class TRT STRATA / param=glm;
Model AVAL = TRT COUNTRY STRATA;
Lsmeans TRT / diff cl exp;
Ods output diffs=lsm_diff;
Run;
```

In cases where separation is a concern for the primary endpoint at Week 8, e.g. 0% or 100% response in one treatment (sub)group, an exact logistic regression model will be applied to all visits. To ensure convergence, this model will not include any continuous covariates.

```
Proc logistic data=aaa exactonly;
Class TRT STRATA / param=glm;
Model AVAL = TRT COUNTRY STRATA;
Exact TRT / estimate=both;
Ods output exactoddsratio=exactoddsratio;
Run;
```

In addition to that the above analysis will also be performed a sensitivity analysis for raw spinal pain NRS score.

Mixed Model Repeated Measures (MMRM)

The following MMRM (or repeated measures ANOVA) model will be used for analysis of raw (total & nocturnal) and average spinal pain NRS score:

```
proc mixed data=.... order=internal;
where vis_1n in (2, 3, 4, 5, 6, 7);
class trt country strata;
model val_1n = trt bsval_1n country strata/ddfm=kr;
repeated vis_1n / subject=sid1a type=un;
lsmeans trt/ cl diff;
```

run;

If type=Unstructured (un) fails, we will use Compound Symmetry (cs)

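### The only sensitivity model listed for the Week 8 primary endpoint has no visit or treatment-by-visit term and an undefined six-value visit list, so it estimates a difference pooled over visits and not the Week 8 effect

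*SAP*

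**What the plan says.** SAP 1.1 sets the time point: "The primary analysis will be performed based on Week 8 assessment data". SAP 2.5.4, under the primary objective, lists one sensitivity analysis: a repeated measures model of the average, total and nocturnal NRS scores with the factors of the logistic model plus the baseline score. On visit it says only "Analysis visit will be used as repeat factor". SAP 2.13 describes the same model, and one "least squares mean difference and 95% confidence interval for the difference in the two treatment groups will be presented along with the p-value". Protocol 9.4.4 names the same factors plus baseline, and no visit term.

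The PROC MIXED code in SAP 5.4.1 follows that text:

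- Visits kept: "where vis_1n in (2, 3, 4, 5, 6, 7".
- Class variables: "class trt country strata".
- Mean model: "model val_1n = trt bsval_1n country strata/ddfm=kr".
- Reported contrast: "lsmeans trt/ cl diff".
- Covariance: unstructured over `vis_1n`, with a fallback: "If type=Unstructured (un) fails, we will use Compound Symmetry (cs".

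Neither document defines `vis_1n`.

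**The concern.** A REPEATED statement shapes the residual covariance. It does not let the mean or the treatment effect vary by visit. The coded model therefore yields one treatment difference averaged over visits, with weights set by the fitted covariance. That equals the Week 8 difference only if the effect is the same at every included visit.

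The visit list is a second problem. Six values are kept, but the placebo-controlled period has five post-baseline visits (Weeks 1, 2, 3, 4 and 8), so one value does not belong.

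This is the only planned inferential model for the continuous NRS scores. The by-visit change-from-baseline summaries are descriptive. The model could understate a real Week 8 effect, or look supportive when the effect is early only.

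**Working it through.** **1. Figures in the plan.** The plan gives no NRS means, SDs or correlations, so there is no figure for this model to reproduce. The sample size does reproduce: the continuity-corrected two-proportion formula (23.5% vs 43.6%, 3:1, 90% power, two-sided 5%) gives 83 placebo patients, and 4 × 83 = 332, as stated. It rests on response rates alone, so this point does not touch it.

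**2. What the coded model estimates.** Every included visit has the same design row (treatment, baseline, country, stratum). With complete data the GLS estimate is therefore exactly

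estimate = Σ w_t d_t, with w = V⁻¹1 / (1ᵀV⁻¹1),

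where d_t is the baseline-adjusted difference at visit t and V is the fitted residual covariance.

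- Compound symmetry (CS): all weights are equal, so the estimate is the simple mean of the d_t.
- Unstructured (UN): weights can be far from equal. If correlation is AR(1) with ρ = 0.8 from Baseline through five equally variable post-baseline visits, V⁻¹1 is proportional to 1 − ρ(1 − ρ), then (1 − ρ)² three times, then 1 − ρ. That is 0.84, 0.04, 0.04, 0.04, 0.20, with sum 1.16. Week 1 gets 0.84/1.16 = 72% of the weight and Week 8 gets 0.20/1.16 = 17%.

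**3. What the values 2 to 7 could mean.**

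| Value | Protocol Table 6-1 visit number | Row order of SAP Table 2-1 (Baseline = 1) |
|---|---|---|
| 2 | Baseline | Week 1 |
| 3 | Week 1 | Week 2 |
| 4 | Week 2 | Week 3 |
| 5 | Week 3 | Week 4 |
| 6 | Week 4 | Week 8 |
| 7 | Week 8 | Week 12 |

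The first reading is the likelier, because SAP 2.2 also calls Week 8 Visit 7. Baseline is then outcome and covariate at once, and its adjusted difference is 0 by construction. Under UN, a baseline slope of 1 with every other coefficient at 0 makes the Baseline residual exactly 0, so that variance can shrink without limit and the likelihood has no finite maximum. In simulation the UN fit was singular in 10 of 10 runs in every scenario. In one traced fit the estimate went −0.176, −0.021, −0.0003 at iterations 5, 10 and 20, while the SE went 0.018, 0.002, 0.00003. The CS fallback would then plausibly apply, and it gives exactly 5/6 of its five-visit value.

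**4. Illustrative size under CS, by hand.** Assumed differences at Weeks 1, 2, 3, 4 and 8, each ending at −1.2:

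| Onset | Differences | Weeks 1–8: mean, share of 1.2 | With Baseline: mean, share of 1.2 |
|---|---|---|---|
| Slow | −0.1, −0.2, −0.35, −0.5, −1.2 | 2.35/5 = 0.47, 39% | 2.35/6 = 0.39, 33% |
| Ramp | −0.3, −0.6, −0.8, −1.0, −1.2 | 3.9/5 = 0.78, 65% | 3.9/6 = 0.65, 54% |
| Fast | −0.8, −1.1, −1.2, −1.2, −1.2 | 5.5/5 = 1.10, 92% | 5.5/6 = 0.92, 76% |

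**5. Simulation of the same trajectories.** 264 vs 88 patients, complete data, country and stratum omitted, 500 trials per setting, SD 2.0–2.5, correlation parameter 0.4–0.6. Pooled estimate as a share of the Week 8 effect:

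- Weeks 1–8: 31–92% (UN), 38–93% (CS).
- Baseline to Week 8: 31–77% (CS).
- Weeks 1–12, with the Week 12 difference at 0–50% of Week 8: 22–85% (UN), 31–85% (CS).
- Week 8 contrast from a model with treatment-by-visit: 99–101%.

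The sign of the pooled estimate was right in at least 96% of trials. The pooled test was significant in 92% or more for ramp and fast onset, but in 47–94% for slow onset. The Week 8 contrast was significant in at least 98% throughout. A repeat run gave about 18–92% for Weeks 1–8.

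For an early-only effect (−0.5, −0.7, −0.6, −0.4, then 0 at Week 8), the pooled test favoured secukinumab in 65–89% of trials and the Week 8 contrast in 2–4%.

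**6. A second set of assumptions.** Post-baseline SD 2.0, Weeks 1–8, UN, 60 trials each. Each pair is for exchangeable correlation 0.6, then AR(1) 0.8.

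| Differences at Weeks 1, 2, 3, 4, 8 | Coded model | With treatment-by-visit, Week 8 |
|---|---|---|
| −0.6, −0.9, −1.0, −1.1, −1.2 | −0.93, −0.76 | −1.19, −1.27 |
| −0.3, −0.5, −0.8, −1.0, −1.5 | −0.82, −0.55 | −1.48, −1.48 |
| −0.1, −0.2, −0.4, −0.6, −1.5 | −0.58, −0.35 | −1.51, −1.48 |
| −1.2 throughout | −1.21, −1.22 | −1.25, −1.19 |

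The step 2 weights explain the AR(1) figure in row 2: 0.724 × 0.3 + 0.0345 × (0.5 + 0.8 + 1.0) + 0.172 × 1.5 = 0.217 + 0.079 + 0.258 ≈ 0.55. Adding a visit main effect alone left the estimate unchanged to three decimals, so the interaction is the term that matters.

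**The case against.** The strongest reply is that no text says this model estimates a Week 8 difference. It already departs from the primary analysis by using continuous scores, an average over the placebo-controlled visits is a legitimate summary in a trial about speed of onset, and the SAP follows protocol 9.4.4. It is true that the purpose is inferred from the model's place under the primary objective. But the SAP does not declare an average-over-visits estimand either, and such an estimand would still need a defined visit list without Baseline as an outcome.

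Other points stand in part:

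- The early-only case is unlikely to mislead a decision. With no Week 8 effect the primary test would usually fail, and protocol 1.1 reports benefit on total spinal pain at all time points up to Week 16 in AS.
- The sizes are assumed and the ranges are not bounds. The second set of assumptions goes down to 0.35/1.5 = 23%, and with ramp or fast onset significance is rarely lost.
- Week 12 is the less likely reading of value 7, and if the input holds no Baseline rows, value 2 does nothing. The missing interaction remains in both cases.
- Leaving `vis_1n` out of CLASS would surface on the first run, because a REPEATED effect must be a class variable. It cannot bias a result.
- Early response is examined elsewhere, through response rates at Weeks 1–4 with confidence intervals.

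**Conclusion.** The concern holds. As written, the sensitivity analysis of a Week 8 endpoint returns a covariance-weighted average over visits, and its six undefined visit values cannot match the five post-baseline visits of Treatment Period 1. Both follow from the text and code without any simulation.

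The size depends on the unknown onset pattern and covariance. Over Weeks 1–8 the pooled value was about 18–93% of the Week 8 effect for the rising trajectories tried, and about 100% only when the effect was constant. With Baseline included and the CS fallback, even a constant effect is cut to 5/6 = 83%.

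This should be fixed, but it is not critical: the primary logistic analysis, the hierarchical BASDAI test and the sample size are unaffected.

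**What to change.** 1. Define `vis_1n`, for example as the analysis visit of SAP Table 2-1, and select outcome records by week: Weeks 1, 2, 3, 4 and 8 only. Baseline is a covariate only, and Week 12 is left out.
2. In CLASS, add `vis_1n` and `sid1a`.
3. In MODEL, add `vis_1n` and `trt*vis_1n`. Adding `bsval_1n*vis_1n` is advisable but optional.
4. Replace the LSMEANS statement with `lsmeans trt*vis_1n / diff cl`. The REPEATED statement can stay.
5. Name the Week 8 LS-mean difference in the average score (95% CI, p-value) as the sensitivity result, and report the same contrast for the total and nocturnal scores.
6. Align SAP 2.5.4 and 2.13, and record the added terms in SAP section 4, which now lists no changes.

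As a check, the repaired model with 6.5–7.8% outcome-dependent dropout (200 trials each) gave Week 8 estimates of −1.22, −1.25 and −1.20 against a true −1.20, and −0.01 against a true 0.

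The cost is SAP wording and code. No new data are needed, and the primary analysis and sample size do not change.

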5.4.2 Key secondary analysis

Not applicable

5.5 Rule of exclusion criteria of analysis sets

Table 1 Protocol deviations that cause subjects to be excluded

Deviation ID	Description of Deviation	Exclusion in Analyses	Severity code
INCL01A	ICF is not signed or missing date of signing ICF	EXCLUDE FROM FAS and SAF	3
INCL01B	ICF date is after visit or assessment date	EXCLUDE FROM FAS	1
INCL01C	Patient unable to understand and communicate with the investigator	EXCLUDE FROM FAS	1
INCL02A	Pregnant or lactating female patients	INCLUDE IN EVERYTHING	0
INCL02B	Age is less than 18 years	EXCLUDE FROM FAS	1
INCL02C	Subject is not diagnosed with axSpA (either AS or nr-axSpA) according to ASAS axSpA classification criteria	INCLUDE IN EVERYTHING	0
INCL02D	Subject with back pain for less than 3 months and/or age on onset at or greater than 45 years.	INCLUDE IN EVERYTHING	0
INCL03	Active axSpA as assessed by BASDAI, BASDAI score is less than 4 or missing at baseline	INCLUDE IN EVERYTHING	0
INCL04	Spinal pain NRS score equal or less than 4 at Baseline	INCLUDE IN EVERYTHING	0
INCL05	Patients do not have at least 2 different NSAIDs at the highest recommended dose for at least 4 weeks in total prior to randomization	INCLUDE IN EVERYTHING	0
INCL06	Patients who are regularly taking NSAIDs as part of their axSpA therapy are not on stable dose for at least 2 weeks before randomization	INCLUDE IN EVERYTHING	0
INCL07	Patients who have previously been on a TNFalpha inhibitor with no appropriate wash-out period prior to randomization	INCLUDE IN EVERYTHING	0
EXCL01	Chest X-ray or chest MRI with evidence of ongoing infectious or malignant process	INCLUDE IN EVERYTHING	0

Deviation ID	Description of Deviation	Exclusion in Analyses	Severity code
EXCL02	Previous treatment with prohibited medication not washed out appropriately before randomization	INCLUDE IN EVERYTHING	0
EXCL03	Previous exposure to secukinumab or other biologic drug directly targeting IL-17 or IL-17 receptor	INCLUDE IN EVERYTHING	0
EXCL04	Patient used investigational drug or devices within 4 weeks before randomization or a period of 5 half-lives of the investigational drug	INCLUDE IN EVERYTHING	0
EXCL05	Subject with history of hypersensitivity to the study drug or its excipients or to drugs of similar chemical classes	INCLUDE IN EVERYTHING	0
EXCL06	Patients previously treated with any biological immunomodulating agents, except those targeting TNFalpha	INCLUDE IN EVERYTHING	0
EXCL07	Patients who have been exposed to more than one anti-tumor necrosis factor alpha (anti- TNFalpha) agent	INCLUDE IN EVERYTHING	0
EXCL08	Patients with previous treatment with any cell depleting therapies including but not limited to anti-CD20 or investigational agents	INCLUDE IN EVERYTHING	0
EXCL09	Pregnant or nursing (lactating) women, confirmed by a positive human chorionic gonadotropin (hCG) laboratory test	INCLUDE IN EVERYTHING	0
EXCL10	Women of childbearing potential, not using effective methods of contraception during the entire study	INCLUDE IN EVERYTHING	0
EXCL11	Patients with active ongoing inflammatory diseases other than axSpA that might confound the evaluation of the benefit of secukinumab therapy	INCLUDE IN EVERYTHING	0
EXCL12	Patients with other ongoing mechanical diseases affecting the spine that may confound evaluation of the benefit of secukinumab therapy	INCLUDE IN EVERYTHING	0
EXCL13	Patients with underlying metabolic, hematologic, renal, hepatic, pulmonary, neurologic, endocrine, cardiac, infectious or gastrointestinal conditions, which immunocompromise the patient.	INCLUDE IN EVERYTHING	0
EXCL14	Patients with significant medical problems or diseases	INCLUDE IN EVERYTHING	0

Deviation ID	Description of Deviation	Exclusion in Analyses	Severity code
EXCL15	Patients with history of clinically significant liver disease or liver injury as indicated by abnormal liver function tests	INCLUDE IN EVERYTHING	0
EXCL16	Patients with history of renal trauma, glomerulonephritis, or patients with one kidney only, or an exceeding serum creatinine level	INCLUDE IN EVERYTHING	0
EXCL17	Patients with abnormal total white blood cell count or platelets or neutrophils or hemoglobin at screening	INCLUDE IN EVERYTHING	0
EXCL18	Active systemic infections during the last 2 weeks prior to randomization (exception: common cold)	INCLUDE IN EVERYTHING	0
EXCL19	Patients with history of ongoing, chronic or recurrent infectious disease or evidence of active tuberculosis infection.	INCLUDE IN EVERYTHING	0
EXCL20	Patients with known infection with human immunodeficiency virus, hepatitis B or hepatitis C at screening or randomization	INCLUDE IN EVERYTHING	0
EXCL21	Patients with history of lymphoproliferative disease or any known malignancy or history of malignancy of any organ system within the past 5 years	INCLUDE IN EVERYTHING	0
EXCL22	Patients with any current severe progressive or uncontrolled disease	INCLUDE IN EVERYTHING	0
EXCL23	Patients with any medical or psychiatric condition, which would preclude the participant from adhering to the study protocol.	INCLUDE IN EVERYTHING	0
EXCL24	Patients with history or evidence of ongoing alcohol or drug abuse within the last 6 months before randomization	INCLUDE IN EVERYTHING	0
EXCL25	Patients with administration of live vaccines 6 weeks prior to randomization or plans for administration of live vaccines during the study period	INCLUDE IN EVERYTHING	0
OTH01	Pregnancy test not performed as required per protocol	INCLUDE IN EVERYTHING	0
OTH02	Spinal pain NRS score at week 8 is missing.	INCLUDE IN EVERYTHING	0
OTH03	Spinal pain NRS score at baseline is missing	INCLUDE IN EVERYTHING	0

Deviation ID	Description of Deviation	Exclusion in Analyses	Severity code
OTH04	Patient PRO data was not collected according to the protocol	INCLUDE IN EVERYTHING	0
WITH01	Pregnant patient not withdrawn from study	INCLUDE IN EVERYTHING	0
WITH02	ICF withdrawn but patient continuing in the study	INCLUDE IN EVERYTHING	0
TRT01	Dosing error in comparative dosing phase (too many injections in treatment phase 1 and 2)	INCLUDE IN EVERYTHING	0
TRT02	Dosing error in comparative dosing phase (less than 2 injections in treatment phase 2)	INCLUDE IN EVERYTHING	0
TRT03	No study medication administered.	INCLUDE IN EVERYTHING	0
TRT04	Patient randomized mistakenly in the study and did not receive study drug.	EXCLUDE FROM FAS and SAF	3
TRT05	The patient was re-randomized to the wrong treatment arm.	INCLUDE IN EVERYTHING	0
TRT06	Patient was randomized to the wrong stratum at baseline.	INCLUDE IN EVERYTHING	0
TRT07	Study medication was administered, which could have been damaged.	INCLUDE IN EVERYTHING	0
COMD01	Prohibited medication consumed during study.	INCLUDE IN EVERYTHING	0
COMD02	Painkillers intake during 24h before a visit involving a disease activity assessment.	INCLUDE IN EVERYTHING	0

Table 2 Analysis set exclusions based on population codes

Analysis set	Population codes that cause a subject to be excluded
RAN	NA
SAF	2, 3
FAS	1, 3

Table 3 Population code text

Population Code	Population code text
0	INCLUDE IN EVERYTHING
1	EXCLUDE FROM FULL ANALYSIS SET (FAS)
2	EXCLUDE FROM SAFETY SET (SAF)

3

EXCLUDE FROM FAS AND SAF

6 Reference

